## 8. Statistical analysis

The study will be reported in accordance with the Strengthening the Reporting of Observational Studies in Epidemiology (STROBE) statement (21). The primary analyses will be descriptive assessments of adherence to unambiguous recommendation in the selected domains of early AP management. Descriptive analysis will be performed where normal continuous variables will be compared via student's t test, and non-normal continuous variables will be compared via Mann-Whitney U test; if >2 categories a one-way ANOVA or Kruskal-Wallis test will be used for normal and non-normal variables respectively, Chi-square tests will be used to detect differences between categorical variables. All analyses will be conducted under a two-tailed hypothesis. Multiple imputation may be used in the case of missing data.

Secondary analyses will evaluate the differences in results according to the hospital. Risk-adjusted funnel plots will be produced to test the performance of individual, anonymised centres for normal rates of primary and selected secondary outcomes. Funnel plots' Y-axes will demonstrate QPI of a management domain and X-axis will show the number of patients admitted in each hospital. Furthermore, differences in clinical outcomes between patients that are managed according to best available evidence (QPI) and those that were not will be explored through mixed effects multivariable logistic models. These models will use the patient at the fixed effect level 1 and the hospital as the random effect level 2 (using the R lmer package) will be performed. A one level, fixed effect binary logistic regression model using a pooled dataset from 5 multiply imputed datasets will also be used in the event of substantial missing data.

Variable selection will be based on statistically significant univariable analysis and those variables deemed clinically significant. Fixed, forced entry will be used to adjust the main outcome measure, The effect of interaction, and sequential removal of non-significant variables will be assessed using changes in Akaike information criteria for multilevel models, and p-values for multiple imputed fixed models.

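### Five imputed datasets are fixed for the case of substantial missing data, which is needlessly few for models whose variables are then dropped by p-value

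*Protocol*

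**What the plan says.** Everything on this point is in Section 8, Statistical analysis, of the protocol.

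- On missing data in general, imputation is optional and no number of sets is given: "Multiple imputation may be used in the case of missing data".
- For the comparison of outcomes between compliant and non-compliant care, the main models are two-level logistic models with hospital as the random level. A one-level fixed-effect logistic model on "a pooled dataset from 5 multiply imputed datasets will also be used in the event of substantial missing data". The number 5 is therefore a stated choice for a named situation.
- Interactions and the stepwise dropping of variables are judged by AIC in the multilevel models, "and p-values for multiple imputed fixed models".
- Tests are two-sided: "All analyses will be conducted under a two-tailed hypothesis". No significance level is stated, although "Variable selection will be based on statistically significant univariable analysis".

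The section does not say how much missing data counts as substantial, and it does not tie the number of imputations to the amount missing.

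**The concern.** The number of imputations matters little when few data are missing and more as the missing share grows. The protocol fixes a low number for exactly the case in which it performs worst.

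Two things follow. First, the between-imputation variance is estimated from 5 values, so the interval uses a t quantile on few degrees of freedom, and the pooled estimate itself carries simulation noise. Second, p-values from these models decide which variables and interactions stay. A variable near the cut-off can stay or go depending on the random seed, and the adjusted estimate for compliance may move with it.

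Substantial missingness is a realistic prospect. Section 5.5 asks for many fields abstracted from charts, including weight, height, administration times and bag-by-bag fluids. Section 6.1 rules out contact with patients. Section 10.2 foresees hospitals that submit badly incomplete data. The models serve a stated secondary aim (Section 2), so their reproducibility has some value.

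**Working it through.** The protocol derives no figure from the number 5, so there is nothing of its own to reproduce. The check asks what 5 costs against larger numbers.

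**Inputs**
- Number of imputations m = 5: protocol, Section 8.
- Two-sided testing: protocol, Section 8.
- Significance level 0.05 and 95% intervals: assumed, since none is stated.
- FMI: assumed, since none is stated. The range 0.1 to 0.5 is shown, with 0.3 to 0.5 as one reading of "in the event of substantial missing data".
- Combination by Rubin's rules: assumed.

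**Interval width.** Set the total variance with unlimited imputations to 1, so that the between-imputation part is FMI and the within part is 1 − FMI. Then

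- T = (1 − FMI) + (1 + 1/m) × FMI
- λ = (1 + 1/m) × FMI / T
- df = (m − 1) / λ²
- width relative to unlimited imputations = t(0.975, df) × √T / 1.96

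Example with FMI 0.3:
- m = 5: T = 0.7 + 1.2 × 0.3 = 1.06; λ = 0.36/1.06 = 0.340; df = 4/0.340² ≈ 34.7; t = 2.031; relative width 1.0668.
- m = 20: T = 0.7 + 1.05 × 0.3 = 1.015; λ = 0.315/1.015 = 0.310; df ≈ 197.3; t = 1.972; relative width 1.0137.
- Ratio 1.0668/1.0137 = 1.052, so 5 sets are about 5% wider than 20.

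| FMI | m = 5 | m = 20 | m = 50 | 5 vs 20 | 5 vs 50 |
|---|---|---|---|---|---|
| 0.1 | 1.0142 | 1.0032 | 1.0013 | +1.1% | +1.3% |
| 0.2 | 1.0365 | 1.0078 | 1.0030 | +2.8% | +3.3% |
| 0.3 | 1.0668 | 1.0137 | 1.0053 | +5.2% | +6.1% |
| 0.5 | 1.1522 | 1.0296 | 1.0114 | +11.9% | +13.9% |

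These widths use the average between-imputation variance. Letting that variance vary at random gives nearly the same result for 5 sets: 1.064 at FMI 0.3 and 1.135 at FMI 0.5.

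Most of the widening is the t quantile. The standard error alone rises, 5 against 50 sets, by √(1.06/1.006) − 1 = 2.6% at FMI 0.3 and √(1.10/1.01) − 1 = 4.4% at FMI 0.5.

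**Seed dependence.** Hold the data fixed and redraw the imputations 200,000 times. The pooled estimate is normal around its limiting value with variance FMI/m. The between-imputation variance is FMI × χ²(m − 1)/(m − 1). The p-value comes from Rubin's t. Take a variable with limiting z = 2.2, that is p = 0.028. Share of seeds giving p ≥ 0.05:

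| FMI | m = 5 | m = 20 | m = 50 |
|---|---|---|---|
| 0.2 | 25% | 4% | 0.1% |
| 0.3 | 35% | 9% | 1% |
| 0.5 | 47% | 21% | 6% |

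With 5 sets, the middle 95% of seeds give p from 0.005 to 0.147 at FMI 0.3 and from 0.002 to 0.223 at FMI 0.5.

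**The case against.** Several objections are fair, and most set limits on the point.

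- **The size depends on an assumed FMI.** No figure in the protocol supports 0.3 to 0.5. FMI belongs to each coefficient and is not the percentage of incomplete records. The option in Section 10.2 to exclude hospitals with badly incomplete data could lower it. At FMI 0.1 to 0.2 the widening is only 1 to 3%. This stands. A reader might infer that the plan's intervals are 6 to 14% too wide; that holds only for FMI 0.3 to 0.5 and a comparison with 50 sets, so it is not a property of the plan.
- **Every finite number of imputations leaves some seed dependence.** This also stands. For a variable sitting almost on the cut-off (limiting p = 0.046, FMI 0.3), the share of seeds with p ≥ 0.05 is 55% with 5 sets, 45% with 20 and 37% with 50, so more sets barely help. Far from the cut-off it hardly matters: at a limiting p of about 0.001, 5 sets cross 0.05 in 0.6% of seeds at FMI 0.3 and 5.8% at FMI 0.5. The gain lies in between, as in the p = 0.028 example.
- **The scope is narrow.** The model is conditional and comes in addition to the multilevel models, which select by AIC. Forced entry and the retention of clinically important variables limit how far p-values shape the covariate set. A reader might infer that the study's compliance result is unstable. The document does not support that, because the primary analysis is descriptive and does not use this model.
- **The combining rule is not stated.** A pooled dataset could mean 5 sets stacked together. Unweighted stacking would make intervals too narrow, the opposite direction. The figures here hold for Rubin's rules, which is why the fix names them.
- **Recording the seed** is a detail that a statistical analysis plan can carry. Its absence from the protocol is no finding.

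None of this gives a reason to keep the number at 5.

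**Conclusion.** The point holds as a modest, cheaply removed weakness. The protocol commits to 5 imputations for the situation where more are most useful, and it lets p-values from those models decide which terms stay. Under Rubin's rules with two-sided 95% intervals, moving from 20 sets to 5 costs about 1% of interval width at FMI 0.1, rising to about 12% at FMI 0.5. For an intermediate variable (limiting p = 0.028) and a 0.05 cut-off, the share of seeds that would drop it is about 35% with 5 sets and 9% with 20 at FMI 0.3, and 47% and 21% at FMI 0.5.

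FMI, the significance level and the combining rule are all assumptions. Intervals from 5 sets remain approximately valid, so what is lost is precision and reproducibility in one supplementary secondary model. There is no bias, and neither the primary result nor the AIC-selected multilevel models are affected. It is an optional improvement.

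**What to change.** In Section 8, replace the number 5 with a rule tied to the missing data: at least as many imputations as the percentage of records missing any variable in the model, and never fewer than 20, with results combined by Rubin's rules. With 30 to 50% of records incomplete, this gives 30 to 50 sets, so the percentage rule, rather than the floor of 20, would usually set the number when missingness is substantial. The floor alone would still leave 9 to 21% of seeds crossing the cut-off in the example above.

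The cost is one changed sentence and a little more computing time. No new data and no change of design are needed.

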## 6.5. Maori Health Directorate

The Whangārei Hospital Māori Health Directorate and [name] offered guidance and advice in the conceptualisation stages of this project. Previous research has shown that Māori have significantly higher rates of AP and diabetes mellitus following ap than non-Māori. In a study of Northland hospitals, a retrospective study found no significant differences in severe AP, mortality or intensive care admission between Māori and non-Māori (20). However, its retrospective design and modest sample size limits the validity of the conclusions, warranting further investigation of this phenomenon.

Ethnicity data will be collected and its impact on the outcomes investigated. If a disparity in outcomes is found it will be imperative that this is reported with the aim of improving outcomes for our Māori patients. Findings (including any preliminary findings) of the study will be discussed early with local research offices who will have systems in place for dissemination to those relevant stakeholders for discussion and action.

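### Section 8 screens, forces and removes covariates without saying which are protected, so confounding of unknown direction may remain in the secondary compliance–outcome models

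*Protocol*

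**What the plan says.** Differences in clinical outcome between patients managed according to the QPIs and those who were not "will be explored through mixed effects multivariable logistic models", with hospital as a random effect (Protocol, Section 8). A one-level logistic model on five multiply imputed datasets is added if missing data are substantial. Covariates for these models are governed by three consecutive statements:

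- Entry: "Variable selection will be based on statistically significant univariable analysis and those variables deemed clinically significant".
- Forcing: "Fixed, forced entry will be used to adjust the main outcome measure".
- Removal: "sequential removal of non-significant variables will be assessed using changes in Akaike information criteria for multilevel models, and p-values for multiple imputed fixed models".

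The software named for the multilevel logistic model is given as "using the R lmer package".

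Three other statements bear on the point:

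- Section 2 (secondary aims) has the outcome comparisons stratified by AP severity.
- Section 6.5 undertakes that "Ethnicity data will be collected and its impact on the outcomes investigated".
- Section 8 limits the primary analysis to description: "The primary analyses will be descriptive assessments of adherence to unambiguous recommendation in the selected domains of early AP management".

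**The concern.** Secondary aims 2 and 3 ask whether compliant care goes with better outcomes. In an observational cohort the answer depends on adjustment for confounders. A significance test against the outcome does not identify confounders. It mainly reflects how many events there are, and here there will be few: Section 1 puts moderate or severe disease at 20%, and ventilation, renal replacement and inotropic support will each be rarer than that.

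The three rules are also not reconciled. Forced entry normally means that a variable stays in whatever its p-value, yet the same sentence goes on to remove non-significant variables and exempts none. Forced entry is tied to the main outcome measure, but the primary outcome is a compliance proportion analysed descriptively, so it is unclear which model is meant. Two analysts could follow the text and report different models. Different removal criteria can also leave the multilevel and imputed models adjusted for different things, so that they no longer check each other.

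Separately, lmer fits linear mixed models, not the logistic ones described.

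**Working it through.** The Protocol gives no sample size, alpha level or effect size for these models, so there is no figure of its own to reproduce. What follows is illustration; each assumed input is labelled.

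**1. Likely cohort size.** From the Protocol: 58 per 100,000 adults per year (Section 1) and three months' enrolment. Assumed: 3.5 to 4.2 million adults and all hospitals taking part.

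- 58/100,000 × 3.5 million ÷ 4 = 507.5
- 58/100,000 × 4.0 million ÷ 4 = 580
- 58/100,000 × 4.2 million ÷ 4 = 609

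**2. Chance that a true confounder fails the screen.** Assumed: a binary confounder with prevalence 30% and OR 2 for the outcome, and a two-sided 0.05 threshold. Let p0 be the outcome rate without the confounder, p1 the rate with it, and n1 = 0.3N, n0 = 0.7N.

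- p1 = 2o/(1 + 2o), with o = p0/(1 − p0)
- power = Φ[(p1 − p0 − 1.96·SE0)/SE1], with SE0 the pooled and SE1 the unpooled standard error

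For N = 500 and p0 = 5%: p1 = 0.0952, pooled rate 0.0636, SE0 = 0.0238, SE1 = 0.0266. Power is Φ[(0.0452 − 1.96 × 0.0238)/0.0266] = 0.479, so the probability of failing is 0.52.

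| N | p0 = 3% | p0 = 5% | p0 = 10% |
|---|---|---|---|
| 300 | 0.76 | 0.67 | 0.50 |
| 500 | 0.66 | 0.52 | 0.30 |
| 600 | 0.61 | 0.46 | 0.23 |

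**3. Effect on the compliance OR, one confounder.** Simulation: N = 500, 1,500 runs, no true compliance effect, baseline outcome rate about 5%, confounder–outcome OR 2, confounder–compliance OR 2.5 in either direction. The confounder is kept only if p<0.05 both in the screen and in the adjusted model.

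| Confounder in compliant patients | Runs losing it | OR, selected | OR, forced | False positives, selected / forced |
|---|---|---|---|---|
| Less common | 56% | 0.94 | 0.99 | 4.5% / 4.7% |
| More common | 58% | 1.05 | 1.00 | 5.5% / 5.1% |
| Unrelated | 50% | 1.01 | 1.01 | 5.3% / 5.3% |

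**4. Effect with eight confounders.** Simulation: n = 580, 800 runs per scenario, no true effect, no hospital effects, log-odds 0.3 per SD on outcome and 0.25 per SD (sign varied) on compliance, p<0.05 screen followed by AIC removal.

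| Scenario | OR, 5% events | OR, 10% events |
|---|---|---|
| All lower compliance, none forced | 0.76 | 0.84 |
| All raise compliance, none forced | 1.31 | 1.18 |
| Alternating signs, none forced | 1.01 | 1.00 |
| All lower compliance, four forced | 0.87 | 0.92 |
| All lower compliance, six forced | 0.95 | 0.94 |

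In the first row false positives were 8% and 10%. In the last three rows they were about 5 to 6%. With 800 runs, a true 5% rate has a standard error of √(0.05 × 0.95/800) = 0.8 percentage points. P-value removal in place of AIC gave 0.76 and 0.85, with 11% false positives at both event rates. The change of removal rule therefore makes little difference to the OR; most of the bias comes from the screen. Full models gave ORs of 0.97 to 1.03.

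**5. Why the two models can differ.** AIC drops a one-parameter term when its likelihood-ratio chi-square is below 2, which corresponds to p above 0.157. Removal at an assumed p>0.05 drops it below 3.84. A covariate with p between 0.05 and 0.157 would stay in the multilevel model and leave the imputed one.

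**The case against.** Much can be said for the plan.

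- The entry rule is not purely statistical: clinically important variables enter whatever their univariable p-value. The text can also be read as forcing those and testing only the rest for removal. On that reading nothing is contradicted. This stands as far as it goes, so the fault is an unresolved ambiguity. But the reading is not written down and the clinical variables are not named.
- A reader might infer that the selection favours compliance, because sicker patients are harder to manage compliantly. The documents give no such sign. The simulated direction only reflects the sign chosen for the confounders, and with mixed signs the net bias vanishes. The sign may also differ by QPI: those on transfer and anticoagulation apply only to severe or predicted severe disease.
- A reader might infer an inflated false-positive rate. It appears only in the worst case. With one confounder, or with half of the eight forced in, the rate stays near 5%.
- Severity, the most obvious confounder, is partly handled by the stratification in Section 2. That helps but does not settle the matter. Section 2 does not say whether predicted or actual severity is meant. Actual severity (Appendix A) rests on organ failure and local complications, which overlap the outcomes. Age, comorbidity and aetiology still need adjustment.
- A reader might infer that ethnicity would never be estimated. Section 6.5 is a separate commitment, and nothing confines ethnicity to these models. What remains is that Section 8 does not protect its adjusted estimate from removal.
- The lmer reference sits beside an explicit statement that the models are logistic, so it is a naming slip.

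**Conclusion.** The point holds in limited form. Section 8 sets out screening, forced entry and sequential removal without saying which variables are forced or exempt, and it uses different removal criteria in the two models. The consequence is possible residual confounding, of unknown direction, in the exploratory analyses for secondary aims 2 and 3, together with models that may not share covariates. The primary outcome is untouched.

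The size depends on inputs that the Protocol does not give. For a single moderate confounder the bias is modest, about 0.94 or 1.05 where the truth is 1. The figures of 0.76–0.84 and 1.18–1.31 are a worst case that needs eight confounders acting in the same direction and none entered on clinical grounds. They should not be quoted as the expected error. The change is worth making because it is cheap, not because a large bias has been shown.

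**What to change.** In Section 8:

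1. Delete the univariable screen and the sequential removal.
2. Before data lock, name one covariate set on clinical grounds from baseline fields already collected. Candidates are sex, ethnicity, and either age or the Charlson index. The index in Appendix E already scores age, so age should not be counted twice. Aetiology is recorded as a final diagnosis in the 30-day section of the form, so include it only where it can be treated as baseline.
3. Avoid severity fields that belong to a QPI or overlap the outcomes. Documented predicted severity is tied to QPI 3 and is undefined for patients in whom no prediction was made. Actual severity shares components with the outcomes. State which severity measure the stratification in Section 2 uses.
4. Force the same set into the multilevel and the imputed models, with a penalised fit for rare outcomes.
5. Replace lmer with a logistic mixed-model routine (glmer).
6. Report the adjusted ethnicity estimate whatever its p-value, in line with Section 6.5.

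This costs wording only and needs no new data. The price is wider intervals for the rarest outcomes: at an assumed 580 patients and 5% events there are about 29 events (580 × 0.05), so ethnicity and aetiology, which have several categories, should be kept coarse. Penalisation eases this but does not remove it.

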## 9. Collaborator roles

### 1. Supervising consultant

Provide guidance for approval processes, provide advice as to registration of the study at the hospital, facilitate communication within the hospital, and mentor and facilitate medical students, junior doctors and registrars in conducting the study at their local site. They have overall responsibility for the site governance registration and should support data collection.

Only one person can fulfil this role. Minimum requirements for authorship include:

- Sponsorship of local study registration, and responsibility to ensure local collaborators act in accordance with local governance guidelines.
- Successful completion of data collection at a centre which meets the criteria for inclusion within the PANORAMA dataset.

Sponsorship through the audit approval/ project registration process by a consultant does not constitute authorship, nor does inclusion of a consultants' patients alone in the audit serves as sufficient for authorship.

### 2. Hospital lead:

This role will ideally be fulfilled by GSET/SET registrar but can be fulfilled by a medical student, junior doctor, trainee, or the consultant supervisor. They will be the single lead point of contact for data collection at each site. They must be responsive to communication from the management team and governance bodies. The hospital lead is the primary person responsible in obtaining local approvals for conduct of the PANORAMA Study. Successful completion of data collection at a centre which meets the criteria for inclusion within the dataset.

### 3. Local collaborators:

A team of up to 8 data collectors per hospital. Minimum requirements for authorship on PANORAMA publications include:

- Compliance with local audit approval processes and data governance policies.
- Active involvement in data collection at a centre which meets the criteria for inclusion.
- Collaboration with the hospital leads to ensure that the audit results are reported *back to the audit office/ clinical teams*.

### 4. Writing and analysis group:

A group of medical students, junior doctors, and external advisory board members responsible for the overall scientific content, data analysis, and preparation of individual research manuscripts.

### 5. Study management group:

This group will manage the running of this study and have overall responsibility for project coordination and data handling.

### 6. Expert advisory group:

A panel of experts who are able to ensure contextual and scientific relevance of the protocol design, data fields, and data interpretation.

## 10. Study completion

### 10.1. Completion

The study will be deemed complete after 4 months (3 months of recruitment and 1 month of follow up) of prospective data collection. The data will then be pooled and analysed by the chief investigator.

